**1. LIST OF ABBREVIATIONS**

ADE	Adverse Device Effect
AE	Adverse Event
AOFAS	American Orthopedic Foot & Ankle Society
CA	Competent Authority
DMP	Data Management Plan
EC	Ethics Committee
FDA	Food and Drug Administration
HA	Hyaluronan / Sodium Hyaluronate / Hyaluronic Acid
HIPAA	Health Insurance Portability and Accountability Act
IA	Intra-articular
ICF	Informed Consent Form
ICH	International Conference on Harmonization
IFU	Instructions for Use
ISO	International Organization for Standardization
ITT	Intent to Treat
MedDRA	Medical Dictionary for Regulatory Activities
OA	Osteoarthritis
PGA	Patient Global Assessment
PI	Principal Investigator
PP	Per Protocol
SADE	Serious Adverse Device Effect
SAE	Serious Adverse Event
SAP	Statistical Analysis Plan
SOP	Standard Operating Procedure
UADE	Unanticipated Adverse Device Event
USADE	Unanticipated Serious Adverse Device Effect

## 2. STUDY SYNOPSIS

Title	A Prospective Study of a Single Injection Cross-linked Sodium Hyaluronate (MONOVISC) to Provide Symptomatic Relief of Osteoarthritis of ankle Joint
Study Objective	Obtain real world, post market data to confirm the clinical improvement and safety in patients treated with a single injection of MONOVISC for the symptomatic relief of osteoarthritis in the ankle joint.
Investigational Product	Monovisc® : A chemically cross-linked sodium hyaluronate supplied as a 4-mL unit dose in a 5-mL glass syringe.
Mode of Delivery	Monovisc will be injected into the intraarticular (IA) space of the index ankle using an 18-22 gauge needle.
Study Design	Prospective, multi-center, open label post market clinical follow up clinical trial.
Phase	Phase IV
Sample Size	25 subjects will be enrolled.
Study Duration	The entire study duration from first subject in to last subject out will be approximately one and half years. The enrollment phase will be approximately 12 months with a follow-up phase of 6 months. Visits will be scheduled at screening, baseline, 1 month, 3 months and 6 months post treatment. First patient in is expected August 2019.
Inclusion Criteria	
Screening Inclusion Criteria
 
 
1. Age 18 years or older
 
2. Body Mass Index (BMI) <math>\leq 35 \text{ kg/m}^2</math>
 
3. Diagnosis of symptomatic osteoarthritic joint in the index joint (Kellgren-Lawrence grade I to III) to be treated with MONOVISC injection.
 
4. Failed conservative treatment for joint osteoarthritis.
 
5. NRS pain on walking <math>\geq 4</math> and <math>\leq 9</math> in the index joint.
 
6. Subject must be willing to abstain from other treatments of the index joint for the duration of the study.
 
7. Subject is willing to discontinue all analgesics including NSAIDs, except acetaminophen/paracetamol, at least seven days before the treatment injection and through the completion of the study.
 
8. Subject is willing to use only acetaminophen/paracetamol (up to a maximum of 4.0 grams per day per the package insert) for the treatment of joint pain for the duration of the study. At least forty-eight hours prior to the Baseline Visit and each follow-up visit, the subject is willing to discontinue use of acetaminophen/paracetamol.
 
9. Subject is willing to maintain a stable dose of oral glucosamine and/or chondroitin sulfate products throughout the study, if taken prior to signing the informed consent form (ICF).
 
10. Able and willing to provide signed informed consent.
 
 
Screening Exclusion Criteria
 
 
1. History of hypersensitivity to any of the ingredients in the hyaluronan
 
2. Infection or skin disease in the area of the injection site or index joint
 
3. NRS pain on walking <math>> 3</math> in the contralateral joint
 
4. NRS pain on walking <math>> 3</math> in the ipsilateral knee or hip
 
5. Subject received an injection of Hyaluronic Acid (HA) and/or steroid in either joint within 6 months of signing the informed consent form (ICF). A subject will be excluded if they are planning to receive an HA or steroid injection (other than the study injection) in either joint during the course of this study.
 
6. Known inflammatory or autoimmune disorders (including rheumatoid arthritis, gout), or other pre-existing medical conditions that, in the opinion of the investigator, could impact treatment of the index joint or affect the ability of the subject to accurately complete the study questionnaires and comply with the study requirements.
 
7. Subject is taking medications at the time of signing the ICF which could interfere with the treatment procedure, healing and/or assessments. This includes but is not limited to oral or injectable anticoagulant treatments, anti-aggregant platelet treatment, chronic opioid analgesics. Low dose aspirin used for cardiovascular protection is allowed if a stable regimen is maintained for the duration of the
 


	
study.
 
8. Subjects who had an oral, intramuscular, intravenous, rectal suppository or topical (excluded in index joint only) corticosteroid prior 30 days of signing the ICF are excluded. Topical corticosteroid use at any site other than the index joint is allowed.
 
9. Significant trauma to the index ankle within 26 weeks of screening
 
10. Chronic use of narcotics or cannabis.
 
11. Ligament instability or tear in index joint.
 
12. Chronic impingement in the index joint requiring surgical treatment
 
13. Diagnosis of fibromyalgia
 
14. Diagnosis of osteonecrosis in index joint
 
15. Subject has significant varus or valgus deformity greater than 10 degrees in either knee.
 
16. Subject requires consistent use of an assistive device (e.g. wheelchair, walker, etc.) Occasional use of a cane is acceptable.
 
17. Uncontrolled diabetes with HbA1c of >7%.
 
18. Subject is a woman who is pregnant or breastfeeding at the Screening Visit or a woman of child bearing potential who refuses to use effective contraception during the course of the study.
 
19. Subject is receiving or in litigation for worker's compensation.
 
20. Otherwise determined by the investigator to be medically unsuitable for participation in this study.
 
Baseline Inclusion Criteria
 
1. NRS pain on walking <math>\geq 4</math> and <math>\leq 9</math>
 
Baseline Exclusion Criteria
 
1. Subject has a decrease of <math>\geq 2</math> in the NRS pain on walking from Screening to Baseline in the index joint.
 
2. Subject has a contraindication to continue with the study treatment injection based on the visual appearance of the synovial fluid aspirate.

Criteria for Evaluation	
Primary Endpoint:
 
 
Reduction of index joint Numerical Rating Scale (NRS) pain on walking from baseline to 6 Months post injection.
 
 
Secondary Endpoints:
 
 
Improvement in AOFAS index from baseline to 6 months post injection.
 
Improvement in Patient Global Assessment (PGA) from baseline to 6 months post injection.
 
OMERACT-OARSI responder rate in the index joint at 6 months post injection.
 
Time to treatment failure
 
Reduction in Medication usage from baseline to 6 months post injection.
 
 
Exploratory Endpoints
 
Any comparisons across timepoints (baseline to 6 months) not described in the primary or secondary endpoints including but not limited to:
 
 
Demographics
 
Medical History
 
History of joint osteoarthritis
 

	
 
• Rescue Medication Use
 
• Treatment Failure
 
• Injection procedure
 
• Concomitant medications
 
• Non-drug therapy
 
 
Safety Endpoint:
 
The incidence, severity, and relationship to treatment of all Adverse Events (AE) will be collected from the first treatment injection to the 6 month assessment.

Statistical Analysis	
The primary analysis on the endpoints will be performed on the ITT (Intent to Treat) populations. All Primary and Secondary endpoints will be analyzed using the ITT population.
 
A secondary analysis will be conducted on the Per Protocol (PP) population. Since the primary endpoint is at 6 months this is all subjects who complete the 6 month assessment and do not have a major deviation in the conduct of the protocol. For all other visits, this is defined as the subjects who complete those visits according to the protocol.
 
All safety analyses will be conducted on all subjects who undergo treatment of MONOVISC in the ankle joint.

Sites	Up to 20 clinical sites in EU
Sponsor	
Anika Therapeutics, Inc.  [name],  United States of America  Phone: + 1 [contact] Fax: + 1 [contact]

### 3. INTRODUCTION

MONOVISC® is Anika's next generation sodium hyaluronate device for treating joint pain. It has been designed to deliver comparable benefits to those of ORTHOVISC® with a single injection.

MONOVISC has previously shown clinical improvement when studied for osteoarthritis of knees. The MONOVISC 07-02 results show MONOVISC achieved a 44% improvement from baseline in WOMAC A scores.

Hyaluronic Acid injections in non-knee synovial joints has been reported to show benefits in pain reduction and improvement in joint function. Patients with hip osteoarthritis had significantly improved Lequesne's function and reduced VAS pain at 3 and 6 months after injection (Migliore et al. *Arthritis Research & Therapy* 2009 Vol 11 No 6). A study on the use of intra-articular HA in the treatment of symptomatic osteoarthritis of the shoulder showed an improvement in VAS score of 24 points from baseline to 6-months (Silverstein et al. *Am J of Sports Medicine*, 2007, Vol 35, No. 6). The effect of a single injection of HA on patients with symptomatic ankle (talo-crural) osteoarthritis show an improvement in VAS score of 44.5 points from baseline to 3 months (Witteveen A.G.H. et al. *J Foot and Ankle Surgery* 2008 Vol 14 p145-152).

The goal of this study is to demonstrate the clinical improvement and safety in patients treated with MONOVISC for ankle osteoarthritis. Specifically, this study will provide confirmation to the effectiveness and safety of MONOVISC at relieving ankle joint pain to 6 months post-treatment.

### 4. BENEFITS / RISKS

#### 4.1 Benefits

Intra-articular injections of MONOVISC and other hyaluronic acid viscosupplements have shown significant clinical benefits for knee osteoarthritis patients. It is anticipated that such benefits may result from the use of MONOVISC to treat ankle OA pain.

#### 4.2 Risks

Any intra-articular injection poses potential risks. However, subjects should incur no additional risks compared to injections of other frequently injected products, such as corticosteroids or diagnostic contrast agents.

Adverse events associated with single intra-articular knee injections of MONOVISC can be found in the MONOVISC Instructions for Use. These events are expected to be similar for ankle injections. In the clinical trial for MONOVISC in knee OA, adverse events that were related to the injection treatment were:

- injection site pain/swelling
- joint stiffness / swelling / effusion
- arthralgia,
- pain in extremity
- synovitis

- contusion
- subcutaneous nodule
- Baker's cyst

Adverse events not related to the index joint for MONOVISC were:

- arthralgia
- headache
- pain in extremity
- upper respiratory tract infection
- back pain

Other risks associated with intra-articular ankle injections, regardless of treatment, include:

- temporary injection site pain, swelling or tenderness
- temporary stiffness of the ankle
- malfunction of the syringe and/or needle

In rare instances, side effects could include:

- an allergic reaction to the fluoroscopic imaging contrast agent. Symptoms could include redness or inflammation at the injection site or inside the ankle joint, hives or itching.
- an allergic reaction to the local anesthetic (lidocaine). Symptoms could include redness or inflammation at the injection site or inside the ankle joint, hives or itching.
- injection site infection
- neurovascular, cartilage, or bone damage resulting from the injection itself

Finally, there is a low risk associated with radiation from the X-ray evaluation required for inclusion in the study. There is also a low risk from the radiation during fluoroscopy-guided injections

## 5. Contraindications / Warnings and Precautions

### 5.1 Contraindications

The following contraindications are included in the package insert (AML 500-263/E):

Monovisc is composed of cross-linked sodium hyaluronate and may contain trace amounts of gram positive bacterial proteins. The following pre-existing conditions may constitute relative or absolute contraindications to the use of MONOVISC

- Known sensitivity to any of the materials contained in MONOVISC
- Pre-existing infections of the skin region of the intended injection site
- Known infection of the index joint
- Known systemic bleeding disorders

### 5.2 Warnings

There are no warnings specific to Monovisc (AML 500-263/E).

### 5.3 Precautions

The following precautions are cited in the package insert (AML 500-263/E):

- Those precautions normally considered during injection of substances into joints are recommended.
- Only medical professionals trained in accepted injection techniques for delivering agents to joint spaces should inject sodium hyaluronate for this application.
- The amount of Monovisc necessary to be injected depends on specific site and patient anatomy and needs to be defined by the medical professional performing the procedure. An excess quantity of sodium hyaluronate should not to be used and the patient should be monitored closely.
- The synovial space should not be overfilled.
- If pain increases during the injection procedure, the injection should be stopped and the needle withdrawn.
- Transient pain or swelling may occur after the intra-articular (IA) injection.
- As with any invasive joint procedure, it is recommended that patients avoid strenuous or prolonged (i.e., more than one hour) weight-bearing activities such as running or tennis within 48 hours following the intra-articular injection.
- **Pregnancy:** The safety and effectiveness of the use of MONOVISC® in pregnant women has not been tested.
- **Nursing Mothers:** It is not known if MONOVISC® is excreted in human milk. The safety and effectiveness of the use of the product in lactating women has not been tested.
- **Pediatrics:** The safety and effectiveness of the use of MONOVISC® in pediatric patients ( $\leq$  21 years of age) has not been tested.

## 6. ENDPOINTS

### 6.1 Primary Endpoint:

- Reduction of index joint Numerical Rating Scale (NRS) pain on walking from baseline to 6 Months post injection.

### 6.2 Secondary Endpoints:

- Improvement in AOFAS index joint from baseline to 6 months post injection.
- Improvement in Patient Global Assessment (PGA) from baseline to 6 months post injection.
- OMERACT-OARSI in the index joint responder rate at 6 months post injection.
- Time to treatment failure
- Reduction in Medication usage from baseline to 6 months post injection.

### 6.3 Exploratory Endpoints

Any comparisons across timepoints (baseline to 6 months) not described in the primary or secondary endpoints, including but not limited to:

- Demographics
- Medical History
- History of joint osteoarthritis
- Rescue Medication Use
- Treatment Failure
- Injection procedure
- Concomitant medications
- Non-drug therapy.

### 6.4 Safety Endpoint:

The incidence, severity, and relationship to treatment of all Adverse Events (AE) will be collected from the treatment injection to the 6 month assessment.

### 6.5 Trial Design

This is a prospective, post market clinical follow-up (PMCF) multi-center, open-label study to evaluate the residual risk of injections of MONOVISC for relief of pain in patients with a diagnosis of an osteoarthritic ankle joint.

The subjects in this study will be patients with a diagnosis of osteoarthritic (OA) joint who the investigator determines are appropriate candidates for treatment with a viscoelastic injection of MONOVISC.

Up to 25 subjects will be enrolled at up to 20 investigational sites in the EU. Subject participation will last approximately 6 Months, with visits scheduled at Screening, Baseline, 1 month, 3 month and 6 months.

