**7.3.9.6 Subject Diary**

Subjects will receive diary for to record rescue medications and concomitant medications.

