### **7.5 Follow-Up Visits**

All study subjects will have follow-up visits at 1, 3 and 6 Months after Baseline to evaluate the joint pain score and to assess adverse events.

The subject should be contacted at least 48 hours prior to their scheduled assessments to be reminded of the required assessment (and applicable wash out period) and to schedule the date and time of contact. At least three documented attempts will be made to contact the subject in order to accomplish maximum subject compliance with the follow-up schedule.

The following tests will be performed at the follow-up visits at 1, 3, and 6 months.

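### Expected early injection reactions are only partly captured before Month 1, and the claim to confirm safety should be limited to describing common adverse events

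*Protocol*

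**What the plan says.** **Aim.** Section 6.5 calls the trial an "open-label study to evaluate the residual risk of injections of MONOVISC for relief of pain in patients". The synopsis gives the objective as "to confirm the clinical improvement and safety in patients treated with a single injection of MONOVISC", and section 3 states that "this study will provide confirmation to the effectiveness and safety of MONOVISC at relieving ankle joint pain to 6 months post-treatment".

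**Safety endpoint.** Section 6.4 names incidence, severity and relationship for all adverse events from injection to Month 6. Section 8.1.1 adds duration, action taken and resolution status.

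**What is expected.** Section 5.3 warns: "Transient pain or swelling may occur after the intra-articular (IA) injection". Section 4.2 lists temporary pain, swelling, tenderness and stiffness. Section 7.4 foresees short-term pain at the injection site. Among rare possibilities, section 4.2 includes "neurovascular, cartilage, or bone damage resulting from the injection itself".

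**How it is collected.** Section 7.4 has one check before the subject leaves on Day 0. After that, section 7.5 says: "All study subjects will have follow-up visits at 1, 3 and 6 Months after Baseline". On the diary, section 7.3.9.6 says: "Subjects will receive diary for to record rescue medications and concomitant medications".

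**Which events count.** The post-treatment part of section 7.4 limits recording, and the request to subjects, to symptoms that were not expected. Section 8.1.1 requires every adverse event during or after injection to be recorded, and names pain, swelling and erythema among the complications of injection.

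**The concern.** The reactions that 25 subjects are most likely to show are local and short, and they fall in the days after the injection. No adverse event contact is scheduled in those days, and the one daily record has no place for symptoms. A site following section 7.4 could also properly leave out an expected swelling that a site following section 8.1.1 would enter. With up to 20 sites and about 25 subjects, such differences would go straight into the incidence table.

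At stake is the safety endpoint itself: how often these reactions occur, how severe they are and how long they last in the ankle. Section 4.2 expects ankle events to resemble those in the knee, and this trial is where that expectation could be checked. A sparse table under an objective of confirming safety would invite a firmer conclusion than the data could carry.

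**Working it through.** **1. The plan's own number.** Section 9.1 sizes the trial on pain alone: change 2, SD 2 to 2.5, 80% power, alpha 5%, n = 15. A one-sample t-test with two-sided alpha 0.05 and SD 2.5 gives n = 15 (power 82.1%), so the figure reproduces. It sets no safety event rate, threshold or precision; 25 is a pain-endpoint number with allowance for dropout.

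**2. Time from discharge to first scheduled recall.** Taking Month 1 as 30 days (an assumption), the ±3-day window in section 7.1 gives days 27 to 33. The ±7-day window in section 7.6 gives days 23 to 37.

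**3. What could record a reaction that starts and ends in the first week.**

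| Route | Section | Covers it? |
|---|---|---|
| Pre-discharge check | 7.4 | Immediate reactions only |
| Spontaneous report | 7.4 | Requested for unexpected symptoms only |
| Indication for a new medicine | 7.3.9.3 | Only if a medicine is started, and not for a pre-existing condition |
| Diary and daily pill count | 7.3.9.6, 7.3.9.2 | Dated paracetamol use, but the drug serves both OA pain (7.3.9.2) and injection-site pain (7.4) |
| Reminder contact | 7.5 | At least 48 hours before the visit, for scheduling and washout |
| NRS and PGA at Month 1 | Appendices 1 and 3 | Look back 24 hours at most |
| Physical evaluation at Month 1 | 7.3.8 | Findings on the visit day |
| Adverse event questioning at Month 1 | 8.1.1 | Yes, from memory |

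For an expected reaction that needed no new medicine, only the last row applies. No rate of early reactions is given, so the shortfall cannot be put in numbers.

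**4. What 25 treated subjects can say about incidence.** With no events in n subjects, the exact two-sided 95% upper limit is 1 − 0.025^(1/n), and the one-sided limit is 1 − 0.05^(1/n).

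- n = 25: 1 − 0.025^(1/25) = 13.7%; one-sided 11.3%.
- n = 20, if enrolment falls short: 16.8%; one-sided 13.9%.

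The chance of at least one case is 1 − (1 − p)^25. The rates p are assumed, since the protocol gives none:

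| True rate | 0.1% | 1% | 2% | 5% | 10% |
|---|---|---|---|---|---|
| P(at least one in 25) | 2.5% | 22.2% | 39.7% | 72.3% | 92.8% |

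Excluding a rate p with one-sided 95% confidence needs ln(0.05)/ln(1 − p) event-free subjects: 29 for 10% and 299 for 1%.

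**The case against.** Much can be said for the plan. Capture is not absent: there is a Day 0 check, subjects are invited to report unexpected symptoms, new-medicine indications become adverse events, pill use is tracked daily, and serious events must reach the sponsor within 24 hours of site awareness (8.1.2). A reaction that persisted would still be found at Month 1. All of this stands, so a reader who inferred that early harms go unrecorded would be going beyond the protocol. Under-counting is a reasonable expectation, not a demonstrated fact.

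Four other stronger readings also fail:

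- That the protocol requires onset to be recorded for each event. Sections 6.4 and 8.1.1 do not mention onset.
- That the rare harms in section 4.2 are declared serious risks of the device. The section does not label them serious, and ties the listed allergic reactions to contrast agent and lidocaine.
- That the trial can say nothing about safety in either direction. Common events can be described, as the 92.8% figure shows.
- That the trial claims to exclude rare harms and so must be larger. It sets no safety hypothesis, and section 9.2.2 plans frequencies and percentages only.

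It is also fair that exact intervals are ordinary content of a statistical analysis plan, which is not at hand, and that any small post-market study has this limit. For that reason the incidence arithmetic is secondary here. The conflict between 7.4 and 8.1.1, the diary content and the wording of the objective, by contrast, are set in the protocol itself.

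**Conclusion.** The point holds as one of incomplete capture. Expected local reactions that resolve before Month 1 depend on spontaneous reports that subjects are asked to make only for something unexpected, on medicine use that does not identify its reason, and on recall after about four weeks. Their incidence, severity and duration are therefore liable to be understated or imprecise. This rests on the reading of the schedule and diary, not on a rate, and no size can be attached to it.

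The contradiction between sections 7.4 and 8.1.1 on which symptoms are recorded needs no assumption.

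The secondary point rests on binomial arithmetic with 25 treated subjects and assumed event rates. Confirmation of safety is too strong a term for a sample in which a clean result leaves rates up to about 14% open. Description of common adverse events is within reach. The primary pain endpoint is unaffected. The change is a cheap improvement worth making.

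**What to change.** 1. Reconcile the post-treatment text of section 7.4 with section 8.1.1, so that every site knows whether expected local reactions are entered as adverse events and subjects are asked to report accordingly.

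2. In section 7.3.9.6, add to the diary dispensed on Day 0 a short daily entry for the first 7 to 14 days: index-ankle pain on a 0-10 scale, swelling and stiffness. Review it at Month 1 and reconcile it with the adverse event log. Pain needs a pre-injection reference, because subjects enter with NRS 4 to 9 and a yes/no item would mostly record existing OA pain. The pre-injection NRS in section 7.4 is already collected and could serve if the diary item uses the same wording.

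3. In the synopsis, section 3 and section 6.5, state the safety aim as describing common adverse events. Give the zero-event upper limit for the number actually treated, since section 6.5 says up to 25 and section 9.1 at least 25.

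**Cost.** No visit or procedure is added. It does need an amendment submitted under section 13.3, some diary data handling and log reconciliation, and slightly more effort from subjects. The recorded rate of minor reactions will probably rise, and the safety statement will be more modest.
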